# 16.2.2.2 Compare Masood Cytology Score value at 0, 12, and 24 months in right and left breast from the same individual in the metformin and non-metformin group:

Women with DCIS will not have two breasts for comparison. We anticipate that this will constitute approximately 25% of the women who participate in this study. Based on our published CALGB study we expect that we will not observe concordance between right and left breast Masood Cytology Score. Our analysis here will further investigate these preliminary observations. A scatter plot (for right vs. left) will be generated to demonstrate dependency between right and left breast Masood cytology scores at each measurement time. Also from each scatter plot, the correlation coefficient and its p-value will be included in this analysis. In order to investigate the time trend in dependency between right and left breast Masood cytology scores, we will compare the correlation coefficients over different time points. We will also make a plot of differences (right-left) or ratios (right/left) over different time-points, and test if there exists any time trend in difference or ratio. The p-value will be calculated accounting for the dependency of the longitudinal data using GEE method.

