#### 2.2 Secondary objectives

- **2.2.1** Use the Masood Cytology Index Score to test for the presence of cytological atypia or disappearance of cytological atypia in RPFNA aspirates after 12 months for both arms, and 24 months (24 month is optional for placebo-only group for patients who remain on placebo arm and will not receive metformin, and mandatory for crossover patients) for women receiving metformin 850 mg p.o. bid (metformin group).
- **2.2.2** Compare Masood Cytology Score values at 0 and 12 months in right and left breasts (if both breasts were aspirated) from the same individual in the metformin and placebo group.
- **2.2.3** Test the reproducibility of RPPM in duplicate RPPM determinations from individual RPFNA specimens.
- **2.2.4** Correlate baseline RPPM values with presence of atypia (as measured by Masood Cytology Index Score) at month 12 and month 24 (month 24 optional for placebo-only group; for patients who remain on placebo arm and will not receive metformin) RPFNA.

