#### 16.2.2 Secondary Objectives:

# 16.2.2.1 Test for Masood score and the presence of atypia or disappearance of atypia in RPFNA after 12 (for both arms) and 24 months for Metformin arm:

We will investigate the trend of Masood score and presence of atypia measured at month 0 and 12 for metformin arm and placebo arm. Breasts will be the sampling units in the analysis of Masood score, while either women (in the primary analysis) or breasts (in the secondary analysis) will be regarded as sampling units in the analysis of atypia. At first, we will perform descriptive analyses for summary statistics of Masood score and atypia at each measurement time. We will also generate a line plot connecting the Masood scores of each breast over time to investigate the time trend.

We will compare the mean Masood scores between 0 vs. month 12 using paired ttests. In this analysis, we will use the breasts as sampling units. The possible dependency between data points from two breasts of each woman will be adjusted using the GEE method using the working independent correlation model. Assuming that about 25% of women (n=11) will contribute one breast and the remaining 75% of women (n=33) will contribute samples from both breasts for each arm, we will have 90% of statistical power to detect a difference of 0.3 times SD if the intracluster correlation coefficients between breasts and two time points are 0.3 for each woman. We will conduct McNemar test to compare the proportion of atypia between month 0 and month 12. These analyses will be conducted for each arm, and the results will be descriptively compared between two arms. We will summarize the 24-month data for the metformin arm.

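### The time-trend test on the signed right-left Masood difference in Section 16.2.2.2 cannot show a change in asymmetry between breasts; orient the pair by baseline and compare arms instead

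*Combined protocol and SAP*

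**What the plan says.** Secondary objective 2.2.2 is to "Compare Masood Cytology Score values at 0 and 12 months in right and left breasts (if both breasts were aspirated) from the same individual"; it covers both treatment arms. Section 11.2 repeats it.

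Section 16.2.2.2 gives the analysis in three parts:

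1. A right-versus-left scatter plot at each visit, for which "the correlation coefficient and its p-value will be included in this analysis".
2. A check of whether that dependency changes: "we will compare the correlation coefficients over different time points".
3. In addition, "a plot of differences (right-left) or ratios (right/left) over different time-points, and test if there exists any time trend in difference or ratio". For this part, "The p-value will be calculated accounting for the dependency of the longitudinal data using GEE method".

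The stated purpose is to follow up an earlier cross-sectional study: "we expect that we will not observe concordance between right and left breast Masood Cytology Score". The heading names both treatment groups, but the body does not say whether the trend test is run by arm, pooled, or with an arm contrast. No alpha, effect size or power is given. In the neighbouring Section 16.2.2.1, "We will compare the mean Masood scores between 0 vs. month 12 using paired ttests", within each arm and with the breast as the unit.

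**The concern.** The third part averages a signed quantity over women. Eligibility (Section 3.3.1) asks for atypia in one or both breasts without naming a side, and the drug is taken by mouth. Women whose worse breast is the right and women whose worse breast is the left therefore cancel. The mean of right minus left stays at zero even if every woman's two breasts become alike, or drift apart.

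Section 1.3.2 reads the low agreement between breasts as a sign that risk may progress at different rates in each breast. A change in that asymmetry is the natural thing to look for, and the signed mean does not measure it. A non-significant trend could be read as evidence that the relation between the breasts did not change. Under exchangeability that result says nothing either way.

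**Working it through.** Section 16.2.2.2 states no power or effect size, so there is no figure of the plan to reproduce.

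**Inputs**

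- Women with two breasts: 75% of 44 = 33 per arm, 66 pooled (Section 16.2.1.2).
- Correlation between breasts: 0.3 (Section 16.2.1.2).
- Alpha: two-sided 5%, stated for the score analysis in Section 16.2.1.2 and assumed here.
- Same-breast correlation from month 0 to month 12: 0.3 (Section 16.2.2.1). A high value comes from the same-day duplicate Spearman coefficient of 0.8312 in Section 1.3.2: 2 sin(π × 0.8312 / 6) = 0.843.
- Entry: worse breast at 14-17 (Section 3.3.1).
- Assumption: within each arm, right and left are exchangeable.

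**Step 1: signed difference.** Let D = R − L at a given visit. If swapping the labels leaves the joint distribution unchanged, E[D] = E[−D], so E[D] = 0 at each visit and the slope is 0. The same holds for log(R/L).

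Example: woman A has right 15, left 12; woman B has right 12, left 15. Suppose the atypical breast falls to 12 in both. The signed differences go from +3 and −3 to 0 and 0. Their mean is 0 before and 0 after, although the asymmetry vanished in both women. Oriented by baseline (higher minus lower), the mean goes from 3 to 0.

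**Step 2: raw ratio.** Averaged over the arbitrary label, the ratio is ½(R/L + L/R) = 1 + (R − L)² / (2RL), which exceeds 1 whenever the breasts differ. For scores 15 and 12 it is 1 + 9/360 = 1.025. If both fall by 3, to 12 and 9, it is 1 + 9/216 = 1.042. The ratio has risen although the difference is still 3.

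**Step 3: simulation of the planned test.** There were 8,000 trials per scenario. Pre-selection scores had assumed mean 13, SD 2 and right-left correlation 0.3, with the worse breast selected at 14-17. A two-sided 5% t-test on the within-woman change from month 0 to 12 stood in for the GEE slope. The six scenarios were: no effect; equal fall in both breasts; response by woman; response by breast; fall in atypical breasts only; growing spread. The simulation error around 5% is √(0.05 × 0.95 / 8000) = 0.0024.

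| Statistic | Rejection, 33 women | Rejection, 66 women |
|---|---|---|
| Signed difference | 0.045-0.054 | 0.049-0.055 |
| Log ratio | 0.046-0.052 | 0.047-0.054 |
| Raw ratio | 0.047-0.125 | 0.053-0.247 |

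An arm-by-time contrast of the signed difference (33 per arm, four effect scenarios) rejected in 0.046-0.057. If exchangeability fails and one side falls 0.25, 0.5 or 1.0 points more than the other, the signed test (33 women) has power 0.16, 0.47 or 0.96.

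**Step 4: why a replacement needs an arm contrast.** The oriented month-0 difference is never negative, so it shrinks without any drug effect. With normal scores, its expected month-12 value is its month-0 value times (ρ_time − ρ_cross) / (1 − 0.3). Here ρ_cross is the correlation of one breast at month 0 with the other at month 12. Taking ρ_cross = 0.3 × ρ_time, the factor equals ρ_time. The expected shrinkage is then 1 − 0.843 = 16% or 1 − 0.3 = 70%, the same in both arms.

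A single-arm trend in the absolute difference is not clean either. In the Step 3 simulation it rejected in 0.18 of trials with no drug effect (33 women). There the month-12 score was the baseline score plus fresh noise, so both the size and the direction of that drift depend on the model.

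**Step 5: power of the oriented contrast.** The month-12 oriented difference was regressed on arm and the month-0 oriented difference, 33 women per arm. Scores had mean 12.34 and SD 2.22, chosen to match Section 14.6.1.2: about 30% atypia (above 13.5) and about 1% suspicious (above 17.5).

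| Effect in the metformin arm | ρ_time = 0.3 | ρ_time = 0.843 |
|---|---|---|
| 40% of women lose 3 points in atypical breasts | about 25% | about 53% |
| 40% lose 5 points in atypical breasts | about 52% | about 77-80% |
| All lose 3 points in atypical breasts | about 91% | about 99% |
| Both breasts fall equally | about 5% | about 5% |

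With no effect it rejects in about 5%. Details of the simulation shift these powers; one implementation at 0.843 gave 42%, 68% and 99%. They are orders of magnitude, not design figures.

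**The case against.** A reader might infer that objective 2.2.2 as a whole is tested with power equal to alpha. The documents do not support that. The correlations and their comparison over time do not depend on the side label. In the Step 3 simulation (33 women) that comparison had approximate power 0.99 when whole women respond, and 0.08-0.23 otherwise. Sections 16.2.1.2 and 16.2.2.1 also test breast-level scores.

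A reader might also infer that a null result is built in for the ratio. It is not: the raw ratio moves, though for the wrong reason.

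Nor does the plan say that this trend tests a metformin effect. Its declared aim is to follow up non-concordance, and the drug effect on score is tested elsewhere, so a null here would not hide such an effect. Objective 2.2.2 speaks of values "from the same individual in the metformin and placebo group", which can be met by reporting each arm and does not demand a formal contrast.

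Finally, the replacement asks a narrower question, whether the worse breast responds more, and has no power if both breasts respond alike. Exchangeability is itself an assumption.

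All of this stands, and it limits the point to one test. It does not rescue that test: the plan states no side-specific hypothesis, and a signed mean is no measure of discordance even for the declared aim.

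**Conclusion.** The concern holds for the trend test alone. Given right-left exchangeability, the signed difference and the log ratio reject at about 5% under every pattern of convergence, divergence or response confined to atypical breasts, by arm or as an arm contrast. The raw ratio departs from 5% only through the level and spread of the scores. The choice between difference and ratio, left open in the text, is therefore between an uninformative test and a misleading one.

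The algebra rests on exchangeability; the power figures for the alternative also rest on the assumed score distribution, the correlation over time and the effect scenarios. Severity is minor: this is one component of a secondary analysis with no stated power.

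**What to change.** In Section 16.2.2.2:

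- Keep the right-left plot as description and drop the trend test on the difference or ratio.
- For women with both breasts sampled at months 0 and 12, define the oriented difference as the breast with the higher month-0 score minus the other. State a rule for ties at month 0.
- Regress the month-12 oriented difference on arm, with the month-0 oriented difference as covariate. Give the estimate with its confidence interval, and summaries by arm as objective 2.2.2 asks.
- Say that this contrast detects only a differential effect between breasts, and that its power is limited and depends on the correlation over time.
- Say which analysis answers objective 2.2.2. Limit the contrast to month 12, the time point in that objective: the section heading adds month 24, by which time placebo women may have taken metformin.

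The cost is SAP wording and one regression on data already being collected.

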# 16.2.2.3 Test the reproducibility of RPPM in duplicate RPPM determination from single bilateral RPFNA specimen:

At each time of month 0 and 12, we will generate duplicated RPPM data on the 50 endpoints. The reproducibility of RPPM at each time point will be tested using (i) unsupervised hierarchical clustering analysis to check if the duplicated data points are clustered together, and (ii) scatter plots between paired RPPM and estimated correlation coefficients. We will use an ANOVA method to test if the intracluster correlation coefficient is 0 or not.

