#### 1.3.5 RPPM analysis of RPFNA cytology

In a single institution study at Duke University, we tested for the reproducibility of RPPM measurements for 53 individual proteins in quadruplicate. RPFNA samples from two independent test sets of 38 and 39 high-risk women. Importantly, there was a high level of community participation in this trial. Of the 77 women enrolled in this trial, 45% (35/77) of women in this trial were African American. Five thousand epithelial cells were Microdissected, solubilized, and tested by RPPM. Duplicate samples were prepared from micro dissection of paired RPFNA aspirates. Fifty of 53 proteins tested by RPPM had an interclass correlation coefficient of agreement of >0.80. These 50 proteins included EGFR, EGFR-pTyr992, EGFR-pTyr1148, ErbB2, ErbB2-pTyr1248, ErbB3, ErbB3-pTyr1289, IGF1R, ER $\alpha$ , ER $\alpha$ -pSer118, IRS1-pSer612, MEK-pSer217/221, ERK-pThr202/Tyr204, HIF1 $\alpha$ , VEGF, GSK3 $\beta$ , AKT-pSer473, mTOR-Ser2448, 4EBP1-pThr37/46, eIF4G-pSer209, 70S6K-pThr412, FKHR-pSer256, IKB-pSer32-36, NF $\kappa$ B(p65)-pSer536, Bad-pSer136, Bcl2-pSer70, 14-3-3- $\zeta$ , p38MAPK, p90RSK, PTEN-pSer380, p53, p21, Stat3, Stat5, Src-pTyr416, Fak-pTyr576, paxillin,  $\beta$ catenin-pThr42/Ser41, Snail-1, vimentin, E-cadherin, pACC-pSer79, and IRS1-pSer612.

**Three high-intensity ER(-) clusters were identified: 1) Cluster #1** activated Akt/mTOR/insulin/Stat3/vimentin: AKTpSer473, mTORpSer2448, 4EBP1pThr37/46, eIF4GpSer209, 70S6KpThr412, p38MAPK, p90RSK, 14-3-3, Src-pTyr416, Fak-pTyr576, Stat3-pTyr694, Stat3-pSer727, vimentin, ACC-pSer79, and IRS1-pSer612. 2) Cluster #2 activated EGFR/MEK/ERK:EGFR, EGFRpTyr1068, MEKpSer217/221, ERKpThr202/Tyr204, HIF1α, VEGF, GSK3β-pTyr279/216, βcatenin-pThr42/Ser41. **3) Cluster #3** mitochondrial survival proteins Bad, Bad-pSer137, Bcl2-pSer270, Bax, Bcl-xl, PTEN-Ser137.

These data demonstrate our ability to test for phosphoprotein expression in mammary cytology from high-risk women. We also provide evidence for our ability to recruit African American women to RPFNA trials. The ability to associate RPFNA cytology with RPPM in a longitudinal study will lead to increased understanding of signaling pathways activated during breast cancer initiation.

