# 14.6.1.4 Reliability of RPPM Measurements (signal to noise, dynamic range, and linearity of RPPM measurements):

- *Signal to Noise Ratio:* For a given protein target (e.g. AKT-pSer473, mTOR, etc.), we scanned the array and the spot intensity normalized relative to total protein calculated using Spyro Ruby fluorescent staining. A standard single value was generated for each sample on the array using Image Quant v5.2 software. Spot intensity was integrated over a fixed area (signal). Local background intensity was calculated for each spot with the unprinted adjacent slide background using JMP v5.0 software (noise). The limit of detection was defined as 2 standard deviations above the background while the functional sensitivity was defined as the lowest signal giving a CV% of less than or equal to 20% within an array; 10 replicates of three defined cell lines were used to estimate the coefficient of variation in the average intensity of each protein. Individual RPPM protein targets that did not fall above 2 standard deviations above background in at least one cell condition were not carried forward in our analysis of RPFNA cytology.
- **Defining the Dynamic Range and Linearity in RPPM:** We tested for the dynamic range and linearity of RPPM for key nodal signaling proteins, through (a) internal serial dilution and (b) a mixture experiment. The range of and

linearity of RPPM protein expression was compared to western analysis. Twenty replicates of a defined standard titration curve [1:0, 1:1; 1:2; 1:5; 1:9; 0:1] were arrayed on each slide. Analysis was performed by taking the mean intensity of 20 individual applications for a given concentration within a slide and comparing it to the mean intensity of the remaining six slides. Analysis of inter- and intraspot reproducibility and linearity showed good correlation (correlation coefficient r2=0.989). There was agreement for the 5 proteins tested AKT-pSer473 (r2=0.999), EGRF (r2=0.982), ERK-pThr204 (r2=0.991), MEK-pSer217 (r2=0.977), and mTor (r2=0.992). These data show strong correlation between RPPM and western analysis.

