#### **16.0 STATISTICAL CONSIDERATIONS AND METHODOLOGY**

#### 16.1 Study Design

#### **16.1.1 Study Populations**

A total of 177 premenopausal women will be pre-registered, among which 96 patients with atypia (Masood Score 14-17) on RPFNA at baseline are expected to be randomized between

Metformin arm and placebo control arm. It is expected that the accrual rate will be 1 patient per month and that accrual will be completed about 8 years after study activation. The randomization will be stratified for known BRCA mutation (BRCA1 or BRCA2 mutation vs. no mutation), prior excisional biopsy (atypical epithelial hyperplasia, atypical lobular hyperplasia, flat epithelial hyperplasia vs. DCIS vs. LCIS), and baseline fasting insulin > 2x ULN vs.  $\leq 2x$  ULN.

At 12 months the women in the placebo arm will be allowed to take metformin. Based on experience from 300 women undergoing serial RPFNA at Duke, it is anticipated that approximately 40% of women who are randomized to the metformin arm will have disappearance of atypia at 12 months and 60% will have persistent atypia. The estimated drop-out rate is 5% at 6 months and 10% at 12 months. Over 98% of women with atypia will have atypia on repeat RPFNA on the non-metformin arm.

We propose to test RPFNA on both right and left breasts at, 12 and 24 months after registration/randomization for the presence or absence (Masood score  $\leq$ 13) of atypia by Masood Cytology Index Score. The RPFNA at 24 months is optional for women who continue on the placebo control arm and will not receive metformin. The outcomes collected at 24 months will be exploratory. In analysis, we will consider taking a transformation, such as logarithm, of positive variables in order to improve the normality and variance stabilization. Among the 96 randomized patients, we expect that about 10% of patients will drop out at month 12. So, the power analyses are based on N= 88 patients (44 per arm).

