#### Alliance A211102

In another exploratory analysis, we will compare the continuous Masood score between two arms. The sampling unit in this analysis will be breast. The change rate (ratio) in Masood score at month 12 from baseline will be compared between metformin group and placebo control group using two-sample t-test for univariate analysis with 2-sided alpha=5%. We will also conduct multivariate analysis to regress the month 12 Masood score on group indicator, age, race, prior excisional biopsy, and baseline Masood score.

Since the sampling unit in this analysis is breast, the Masood score observations from two breasts may be potentially correlated. In order to account for possible dependency between the data points from two breasts of each woman, the variances of t-test (in univariate analysis) and regression estimates (in multivariate analysis) will be estimated using the GEE.

It is expected that about 25% of women (n = 11) will contribute one breast and the remaining 75% of women (n = 33) will contribute samples from both breasts, so that there will be about 77 (= 11x1 + 33x2) data points (breasts) per arm in this analysis. Assuming that the intracluster correlation coefficient between two breasts is 0.3, this analysis will have 84% power to detect a difference of 0.4 times the standard deviation (SD).

Similar analyses will be conducted for 24 months data.

The women or breasts with unsatisfactory repeat RPFNAs will be considered missing at random in the analysis.

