# 16.2.2.4 Correlate baseline RPPM values with presence of atypia at month 12 and month 24:

We will combine data set of metformin and no-metformin groups (N = 88) and use the breasts as the sampling units in this analysis. The possible dependency in observations between the left and right breasts for each woman will be adjusted using the GEE approach.

The baseline RPPM value of each protein will be correlated with Masood cytology score at month 12 using a simple linear regression method. In a multivariate analysis, Masood score at month 12 will be regressed on the baseline RPPM value of each protein, group indicator, age, race, prior excisional biopsy, and baseline Masood scores. Similar analysis will be conducted using the change rate of Masood score between baseline and month 12 in place of Masood score at month 12.

The baseline RPPM value of each protein will be correlated with presence and absence of atypia at month 12. A total of 50 proteins will be tested, so that the significance of each protein will be adjusted for multiple testing by controlling the family-wise error rate (FWER) using the permutation method. We expect that about 60% of the women will have persistent atypia at 12 months. The 50 proteins were selected from a previous study so that they are expected to have reasonable effect sizes. Assuming that each woman contributes samples from only one breast and the proteins have correlation coefficient of 0.1, the multiple testing procedure controlling the FWER at 10% level by two-sided tests will have about 90% probability to detect 15 or more proteins if 25 of the 50 proteins have an effect size of 0.8 times SD [Jung and Young, 2011]. Since about 75% of women are expected to contribute samples from both breasts to the study, the real power for this analysis will be higher.

In a multivariate analysis, presence of atypia at month 12 will be regressed on the baseline RPPM value of each protein, group indicator, age, race, prior excisional biopsy, and baseline Masood scores.

A similar analysis will be conducted to correlate baseline RPPM value of each protein with Masood score and presence/absence of atypia at month 24.

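### The only formal test of RPPM reproducibility asks whether the ICC is zero, a bar that half-noise proteins clear; conclusions should rest on the ICC with its 95% CI

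*Combined protocol and SAP*

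**What the plan says.** Section 2.2.3 sets the objective: "Test the reproducibility of RPPM in duplicate RPPM determinations from individual RPFNA specimens". Section 16.2.2.3 plans duplicate data on 50 endpoints at months 0 and 12 and lists three analyses:

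- hierarchical clustering, to see whether duplicates fall together;
- "scatter plots between paired RPPM and estimated correlation coefficients";
- a test: "We will use an ANOVA method to test if the intracluster correlation coefficient is 0 or not".

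Only the third has a null hypothesis. The section gives no alpha, number of pairs, confidence interval, level of acceptable agreement or multiplicity rule. The family-wise error control in section 16.2.2.4 ("A total of 50 proteins will be tested, so that the significance of each protein will be adjusted for multiple testing") belongs to a different question, the association of baseline RPPM with atypia.

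Two other sections bear on reliability. Section 1.3.5 reports an earlier study by the size of the coefficient: "Fifty of 53 proteins tested by RPPM had an interclass correlation coefficient of agreement of >0.80". Section 14.6.1.4 describes earlier checks of detection limit, coefficient of variation and linearity, with this filter: "Individual RPPM protein targets that did not fall above 2 standard deviations above background in at least one cell condition were not carried forward".

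**The concern.** Two determinations from one specimen share the same cells, so some correlation is expected before any data are seen. Reproducibility is a question of how closely they agree, and a test against zero does not address it. A protein whose duplicates are half replicate error can receive the same verdict as one that is highly repeatable.

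At stake is what the trial can say on objective 2.2.3. A summary that nearly all 50 endpoints are significantly reproducible could come from an assay with an ICC near 0.50. There is also a smaller effect on section 16.2.2.4. Measurement noise there mainly costs power, so a null association is easier to interpret if the reader can see how repeatable that protein was.

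**Working it through.** The plan gives no figure for this test, so there is none to reproduce. The check asks what the test can distinguish.

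**Inputs**
- Replicates per specimen: k = 2 (section 16.2.2.3).
- Month 12, one breast per woman: 88 pairs. Section 16.1.1 says "Among the 96 randomized patients, we expect that about 10% of patients will drop out at month 12" and bases power on 88.
- Month 12, both breasts where available: section 16.2.1.2 says "so that there will be about 77 (= 11x1 + 33x2) data points (breasts) per arm in this analysis", so 2 × 77 = 154 pairs.
- Month 0: 96 women, so 96 pairs with one breast each. At the same 25%/75% split, 24 × 1 + 72 × 2 = 168 pairs.
- Assumed: alpha 0.05, with 0.05/50 = 0.001 as the strict alternative; pairs independent; every pair usable. As usable pairs may be fewer, 40 is added as a further assumption.

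**Formulas** (one-way ANOVA, n pairs)
- Observed F = (1 + ICC)/(1 − ICC), on n − 1 and n degrees of freedom.
- Smallest observed ICC that rejects: (Fcrit − 1)/(Fcrit + 1).
- At a true value ρ, F divided by (1 + ρ)/(1 − ρ) follows a central F distribution, which gives the rejection probability.
- 95% CI: divide the observed F by the 97.5% point of F(n − 1, n), or multiply it by the 97.5% point of F(n, n − 1), then convert back.

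Example, n = 88: Fcrit = 1.424, so the smallest rejecting ICC is 0.424/2.424 = 0.175. At ρ = 0.50 the scale factor is 1.5/0.5 = 3. The test therefore rejects when a central F exceeds 1.424/3 = 0.475, which has probability 0.9997.

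**Results at alpha 0.05**

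| Pairs | Smallest rejecting ICC | Rejects at true 0.10 | 0.20 | 0.30 | 0.50 | 0.80 |
|---|---|---|---|---|---|---|
| 40 | 0.258 | 15% | 35% | 61% | 96% | >99.9% |
| 88 | 0.175 | 24% | 60% | 89% | >99.9% | >99.9% |
| 96 | 0.167 | 25% | 63% | 91% | >99.9% | >99.9% |
| 154 | 0.132 | 34% | 81% | 99% | >99.9% | >99.9% |
| 168 | 0.127 | 36% | 83% | 99% | >99.9% | >99.9% |

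**Sensitivity**
- At alpha 0.001 with 88 to 168 pairs, rejection is 1.5% to 3.6% at a true ICC of 0.10, 41% to 81% at 0.30, and 98% to over 99.9% at 0.50. With 40 pairs it is 61% at 0.50 and over 99.9% at 0.80.
- Correlation between a woman's breasts of 0, 0.3 or 0.6 (20,000 simulated trials, true ICC 0.30, alpha 0.05) gives 98.5%, 98.4% and 98.4% with 154 breasts, and 99.0%, 99.0% and 98.9% with 168.

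**What an interval would show.** At an observed ICC of 0.50 the 95% CI is 0.33 to 0.64 with 88 pairs and 0.38 to 0.61 with 168. At 0.80 it is 0.71 to 0.86 with 88 pairs and 0.74 to 0.85 with 168. These intervals separate 0.50 from 0.80 clearly, where the test against zero does not.

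**The case against.** **Much of the substance is already planned.** This is largely right. The plots and estimated coefficients would expose gross differences between proteins, and the ANOVA itself yields an ICC estimate. A reader might infer that the plan has no measure of agreement at all; section 16.2.2.3 does not support that. What remains is that no interval is planned and the coefficient is not named. If it is a Pearson coefficient, it would miss a constant shift between the first and second determination.

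**The test is not empty.** This also stands. At an ICC of 0.10 it rejects only 24% to 36% of the time, so it flags proteins that are close to pure noise. To call it worthless would go too far.

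**The pair counts are assumed, and 88 is not a true minimum.** Agreed: section 16.2.1.2 anticipates unsatisfactory repeat aspirates. With 40 pairs, rejection at an ICC of 0.30 falls to 61%, but at 0.50 it is still 96%. The test begins to separate 0.50 from 0.80 only if few pairs are combined with a strict alpha, and the plan specifies neither.

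**The earlier 0.80 is not a fair yardstick.** A reader might take section 1.3.5 as setting an acceptance level that the planned test fails to apply. The documents do not say so. That section reports a prior result from quadruplicate measurements, with duplicates prepared from paired aspirates, in high-risk women. This trial takes duplicates from individual specimens in women restricted to a Masood score of 14 to 17 and a BMI of at least 25. An ICC depends on the spread between subjects. If that variance were halved (an assumption), an ICC of 0.80 would become 0.40/(0.40 + 0.20) = 0.67 with no change in the assay. A count of estimates above 0.80 would also be a poor rule in itself, because a protein with a true ICC of exactly 0.80 passes it about half the time.

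**Assay validation has been done.** The section 14.6.1.4 work used cell lines and titration curves. It does not measure duplicate agreement in this trial's specimens.

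**Conclusion.** The concern holds in a limited form. The one formal test for objective 2.2.3 sets a low bar: it can show that duplicates are related, but not that they agree. With 88 to 168 independent pairs and alpha 0.05, all assumed, it treats a protein with a true ICC of 0.50 and one with 0.80 alike. The descriptive analyses partly fill the gap, but without an interval.

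The consequence is small. A reader might infer that the protein associations in section 16.2.2.4, or the trial's main result, are undermined. Neither follows: no protein is selected or dropped on the basis of this test, noise there mainly reduces power, and the primary endpoint is cytological atypia, which does not use RPPM. This is a worthwhile but minor improvement to a secondary laboratory objective.

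**What to change.** In section 16.2.2.3:

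- Keep the clustering and scatter plots.
- Base conclusions on objective 2.2.3 on the ICC of agreement between duplicates with its 95% CI, for each of the 50 endpoints at months 0 and 12. Where both breasts contribute, obtain the CI by resampling women.
- The test of ICC = 0 may stay as a minimal screen, with a sentence saying that rejection is not evidence of reproducibility.
- Do not count estimates above 0.80. Cite section 1.3.5 only as context, noting its different replicate scheme and population.
- If the sponsor wants a pass mark for the lower limit, set it before the data are analysed. Its value is the sponsor's choice.

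In section 16.2.2.4, show each protein's ICC beside its result, and exclude no protein on that basis.

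**Cost.** A wording change and 50 × 2 = 100 ICCs with intervals, with no new patients, specimens or assays. The downside is that fewer proteins may look reproducible. Purely as an illustration, a lower 95% limit above 0.80 would be reached 31% (88 pairs) to 53% (168 pairs) of the time at a true ICC of 0.85, and 94% to 99.8% of the time at 0.90.
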